6.0 STUDY DRUG AND CONCOMITANT THERAPIES

6.1 **Study Drug**

6.1.1 **Study Drug Description and Supply**

The QR-421a study drug is a solution for IVT injection.

Please refer to the Pharmacy Manual and Study Reference Manual for additional details.

6.1.2 **Placebo**

No placebo is used.

6.1.3 **Study Drug Shipment and Storage**

Please refer to the Pharmacy Manual for details on shipment, storage, handling, preparation and administration.

6.1.4 Study Drug Accountability and Reconciliation

The Investigator must designate a research pharmacist or other staff member to maintain an inventory record of drugs received and dispensed. Additional details on study drug accountability are provided in the Pharmacy Manual and the Study Reference Manual.

Forms are provided to facilitate the inventory control. These forms must be used unless the Investigator (or designee) has previously established a system that complies with local regulations and is approved by the Sponsor. The study drug must be dispensed only at the institution(s) specified on form Food and Drug Administration (FDA) 1572 or Statement of Investigator (as applicable).

ProQR Therapeutics Page 32 of 67 Upon completion or termination of the study and after inventory by a Sponsor representative (monitor), it will be determined if unopened study drug vials are to be sent to the Sponsor in the original containers or are to be destroyed at the study center.

6.1.5 **Dosage and Administration**

Two dose regimens of QR-421a will be tested:

- 1. 180 μg loading dose, 60 μg maintenance dose (180/60 μg)
- 2. 60 μg loading dose, 60 μg maintenance dose (60/60 μg)

The physician administering study treatment will be unmasked to assignment of study drug or sham-procedure but will be masked to the dose of study drug. Treatment assignment will be through the centralized Interactive Web Response System (IWRS) for the study. The physician performing the clinical assessments will be masked. All subjects will be masked to study treatment assignment.

Subjects will receive QR-421a via IVT injection or will undergo a sham-procedure. Administration of QR-421a and the sham-procedure will only be performed by qualified ophthalmologists in an in-clinic setting. No other medications should be mixed with QR-421a.

Reference is made to the Study Reference Manual and Pharmacy Manual for detailed instructions on the IVT injection and the sham-procedure.

6.2 **Concomitant Medications and Auxiliary Therapy**

There are no medicinal products classified as auxiliary in this clinical trial.

6.2.1 **Prohibited Concomitant Medications**

The use of any investigational drug or device within 90 days or 5 half-lives of the drug at Day 1, whichever is longer, or plans to participate in another clinical study during the study period is prohibited. Medications that are known to be toxic to the lens, retina, or optic nerve are prohibited. These may include, but are not limited to systemic/intraocular steroids, amiodarone, deferoxamine, chloroquine/hydroxychloroquine sulfate, tamoxifen, phenothiazines, and ethambutol, pentosan polysulfate, etc. Topical steroids are not prohibited but should only be used following consultation with the Medical Monitor.

During the study, use of any new medication or change in the dose of a medication that may have side effects on vision will need to be reviewed and approved by the Medical Monitor.

ProQR Therapeutics Page 33 of 67

6.2.2 **Adequate Forms of Birth Control**

Women of childbearing potential (WOCBP; ie, fertile, following menarche and until becoming postmenopausal unless permanently sterile) and fertile male subjects (ie, after puberty unless permanently sterile) must either practice true abstinence in accordance with their preferred and usual lifestyle, or agree to use highly effective methods of contraception for up to 24 months following their last dose of QR-421a. A postmenopausal state is defined as no menses for 12 months without an alternative medical cause. Permanent sterilization methods include hysterectomy, bilateral salpingectomy, and bilateral oophorectomy. A man is considered fertile unless permanently sterile by bilateral orchiectomy or has undergone vasectomy and received medical assessment of surgical success.

Highly effective methods of birth control include:

- Combined (estrogen and progestogen containing) hormonal contraception associated with inhibition of ovulation (oral, intravaginal, transdermal)
- Progestogen-only hormonal contraception associated with inhibition of ovulation (oral, injectable, implantable)
- Intrauterine device
- Intrauterine hormone-releasing system
- Bilateral tubal occlusion
- Vasectomized partner (provided that the partner is the sole sexual partner and has received medical assessment of the surgical success)
- Sexual abstinence: sexual abstinence must be true abstinence which is the preferred and usual lifestyle of the subject. Periodic abstinence (eg, calendar, ovulation, symptothermal, post-ovulation methods), declaration of abstinence for the duration of the study, and withdrawal are not acceptable methods of contraception

Double barrier methods (a combination of condom with cap, diaphragm, or sponge with spermicide) are not considered highly effective.

Women of non-childbearing potential (ie, not fertile, before menarche, postmenopausal, or permanently sterilized) may be included without the use of adequate birth control, provided they meet the criteria in the protocol.

Birth control measures must be employed during the time of participation (beginning at the Screening Visit) in this study and must be continued

ProQR Therapeutics Page 34 of 67 A man who is fertile should use a condom during treatment and until

7.0 **STUDY VISITS**

All study visits, assessments and procedures should be completed as indicated per the SOE

7.1 Visit and Assessment Windows

For those procedures for which a specific time point post dose is required (eg, systemic exposure blood draws), the protocol refers to nominal times. Actual times for such assessments are to be recorded in the source documentation and in the eCRFs, and if any time points are missed, the reasons are also to be recorded. For more details, please refer to the case report form completion guidelines.

Visits and/or assessments can be completed over multiple, non-consecutive days.

All efforts should be taken to prevent missing data. Therefore, deviations from the treatment cycle (and subsequent assessments) may be justified in some cases, eg. if an AE makes treatment impossible at the schedule dosing day. In exceptional cases, eg, related to the significant restrictions in site activities or subject's ability to travel to sites for visits as occurring related to the COVID-19 pandemic, extensions of the visit window or alterations in the SOE can be approved by the Medical Monitor. Such extensions of the visit window will be documented as protocol deviations. Still, sites should make every reasonable effort to complete scheduled visits within the time windows defined in this protocol.

7.2 Screening

Prior to or at the first Screening visit a sample for gene sequencing analysis will be obtained (see Section 8.55 for further details). In case the sample for gene sequencing analysis will be obtained prior to the first Screening visit, a separate Informed Consent Form (ICF) and/or assent is available for this purpose (see Section 12.2).

ProQR Therapeutics Page 35 of 67

During the screening period, subjects will be assessed according to the eligibility criteria and specified assessments conducted, as presented in the SOE Subjects who have been identified as screen failure may be rescreened if, in the opinion of the Investigator, there is a reasonable chance that the subject may become eligible at a later timepoint. If the decision is taken to rescreen a subject, the subject will need to be re-consented and will obtain a new subject number.

For all subjects, screening should be conducted in a stepwise manner so that eligibility is confirmed first by less intensive assessments. More intensive assessments are to be conducted once eligibility by other criteria have been confirmed to minimize risk and burden.

7.3 **Dosing and Follow-up Visits**

The timing of dosing and follow-up visits is outlined in the SOE . Study treatment will be administered by unmasked qualified ophthalmologists.

All follow-up study visits, assessments and procedures should be completed as indicated per the All efforts should be taken to prevent missing data. Deviations from the SOE treatment cycle (and subsequent assessments) may be justified in some cases, eg. if an AE makes treatment impossible at the scheduled dosing day (see also Section 7.1). Subjects will be assessed for safety, tolerability, and efficacy at follow-up visits with all ophthalmic assessments performed on both the study eye and fellow eye.

7.4 End of Study Visit & Roll Over to Open Label Extension Study

8.0 STUDY ASSESSMENT PROCEDURES

All clinical assessments (including all efficacy and safety assessments) will be performed by masked staff. Clinical monitoring during and right after administration of study treatment will be performed by an unmasked IVT physician (see also Section 4.2.1.3).

ProQR Therapeutics Page 36 of 67

Eligible subjects must complete all Screening examinations. If a subject is unable to complete a specific assessment, this should be recorded in the eCRF and the subject's ability reassessed at the next specified visit. All attempts at performing assessments should be recorded in the eCRF. Any assessment may be repeated if the results are considered unreliable or of unacceptable quality by the Investigator.

8.1 Efficacy

Efficacy assessments include BCVA, LLVA, SD-OCT, static perimetry, FST, mobility course (at selected sites) and PROs. A central reading center, utilizing evaluators masked to treatment assignment, will assess static perimetry, FST, and SD-OCT. Mobility course scoring will also be reviewed and calculated by a masked evaluator. See the Study Reference Manual, Imaging Procedure Manual and Mobility Course Manual for further information on these assessments.

Subjects' assessment of the impact of their visual disability on general health-related outcomes as well as specific vision-related outcomes of daily living will be assessed by the MRDQ (at selected sites) (Lacy 2021).

Subjects' assessment of disease severity will be assessed by PGI-S, and assessment of any improvement or decline in clinical status will be assessed by PGI-C.

8.2 Safety

Safety assessments to monitor for AEs include ophthalmic examinations, laboratory evaluations, and SD-OCTs. Assessments will be conducted as indicated by the SOE

8.2.1 **Adverse Events**

Information regarding occurrence of AEs will be captured throughout the study. Duration (start and stop dates), severity/grade, outcome, treatment, and relationship to study drug will be

ProQR Therapeutics Page 37 of 67 recorded. Refer to Section 9.0, Assessment of Safety or Adverse Events and Serious Adverse Events, for further details.

8.2.2 **Laboratory Evaluations**

All laboratory evaluations will be conducted at a central laboratory. Reference ranges for all laboratory parameters are provided in the Laboratory Manual. See Appendix 2 for a list of laboratory tests to be conducted.

Serum chemistries will include sodium, potassium, chloride, bicarbonate, blood urea nitrogen (BUN), creatinine, glucose, calcium, phosphorus, alanine aminotransferase (ALT), aspartate aminotransferase (AST), gamma-glutamyl transferase (γGT), C-reactive protein (CRP), alkaline phosphatase (ALP), total and direct bilirubin, lactic dehydrogenase (LDH), albumin, and total protein. Estimated glomerular filtration rate (eGFR) is to be calculated using the CKD-EPI Creatinine Equation 2009 calculation.

Hematology will include a complete blood count (CBC): CBC with absolute differential (hematocrit, hemoglobin, white blood cell count [WBCs], red blood cell count, neutrophils, lymphocytes, monocytes, eosinophils, basophils, platelet count).

Coagulation panel: prothrombin time and International Normalized Ratio (INR).

For female subjects of childbearing potential, a pregnancy test will be performed as indicated by and is recommended at any visit that may warrant a pregnancy test. the SOE

Eligibility of the subject to participate in the study is based in part on safety signals that may be indicated by laboratory values.

Repeat laboratory tests are permitted to confirm potentially spurious values or false positive results, at the discretion of the Investigator. Repeat analysis results for any laboratory assessments that are eligibility criteria should be discussed with the Medical Monitor prior to subject inclusion.

8.2.3 **Ophthalmic Examinations**

Ophthalmic examinations include slit lamp biomicroscopy, intraocular pressure, and dilated fundus examination and will be performed as indicated per the SOE

ProQR Therapeutics Page 38 of 67

Further details on the procedures for ophthalmic examinations are in the Study Reference Manual.

8.2.4 **Spectral Domain Optical Coherence Tomography**

Changes in SD-OCT findings, . All SD-OCT scans should be performed in accordance with the procedures outlined in the Imaging Procedure Manual.

8.3 **Systemic Exposure**

Blood samples for systemic exposure analysis of QR-421a will be collected from all subjects as indicated per the SOE-

8.4 **Immunogenicity**

Blood samples for assessment of immunogenicity will be taken as indicated per the SOE and stored for potential later quantification.

8.5 **Gene Sequencing**

A genotyping report (either historic or at screening) is required for eligibility. A blood or saliva sample for genotyping and gene sequencing should be obtained at or prior to the Screening Visit. In case the sample for gene sequencing analysis will be obtained prior to the first Screening Visit, a separate Informed

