5.0 SELECTION OF STUDY POPULATION

5.1 **Study Population**

Subjects with a diagnosis of RP due to mutations in exon 13 of the USH2A gene who meet all eligibility criteria will be eligible for participation in this study.

5.2 **Selection of Subjects**

Screening of subjects will be performed within 12 weeks prior to dosing.

Subjects will be evaluated against all eligibility criteria as presented in the SOE

If a subject would not be eligible in the opinion of the Sponsor's Medical Monitor, after discussion with the investigator it may be decided that the subject cannot participate in the study.

Results of assessments for all eligibility criteria must be available and reviewed prior to the subject's dose of study treatment.

5.3 **Eligibility Criteria**

OR

5.3.1 **Inclusion Criteria Relating to Study Initiation**

The subject is eligible for the study and thus eligible to receive QR-421a or sham-procedure in the study eye if all the following inclusion criteria apply at Screening/Day 1:

- 1. An adult (\geq 18 years) willing and able to provide informed consent for participation prior to performing any study related procedures, and suitable verbal, auditory, written and/or tactile sign language communication as to allow informed consent to be obtained, in the opinion of the Investigator.
 - A minor (12 to < 18 years) with a parent or legal guardian willing and able to provide written permission for the subject's participation prior to performing any study related procedures and pediatric subjects able to provide age appropriate assent for study participation.
- 2. An adult willing to comply with the protocol, follow study instructions, attend study visits as required and willing and able to complete all study assessments. OR
 - A minor able to complete all study assessments and comply with the protocol, and has a parent or caregiver willing and able to follow study instructions, and attend study visits with the subject as required.
- 3. Clinical presentation consistent with RP with Usher syndrome type 2 or non-syndromic form of RP (NSRP), based on ophthalmic, audiologic, and vestibular examinations.
- 4. A molecular diagnosis of homozygosity or compound heterozygosity for 1 or more pathogenic exon 13 mutations in the *USH2A* gene, based on genetic analysis at screening.

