10.6 Subject Disposition, Demographics and Baseline Disease Characteristics

Subject disposition will be summarized for All Screened Subjects population by dose group.

The number and percentage of subjects who receive QR-421a or the sham-procedure will be tabulated by the number of doses and the treatment group.

Subject demographics and baseline characteristics will be summarized for each treatment group and for all subjects combined. Subject characteristics at baseline include age, race, body weight, and height. Baseline disease characteristics include ophthalmic examinations, measurements, and tests, as previously described.

10.7 **Treatment Compliance**

All doses are observed and administered by study staff. Treatment compliance will be determined by source records documenting treatment observations and summarized.

10.8 **Efficacy Analyses**

The efficacy evaluations will include evaluations of the endpoints listed in Section 4.1.

Descriptive statistics of clinical efficacy will be tabulated by dose group, and if appropriate, for dose groups combined.

All continuous endpoints will be summarized using the following descriptive statistics: number of subjects, mean, standard deviation, standard error, median, minimum, maximum and 95% confidence intervals for the mean. Categorical endpoints will be summarized using the following: number of subjects, frequency, percentages and 95% confidence intervals. If data appear highly skewed, natural log or other transformation may be used to compute summary statistics.

Continuous efficacy endpoints will be summarized and may be analyzed using appropriate parametric or nonparametric inference tests.

ProQR Therapeutics Page 50 of 67

Investigational Product: QR-421a Protocol No. PQ-421a-004 (Version 2.0)

10.9 **Safety Analyses**

10.9.1 **Treatment Emergent Adverse Events**

A treatment-emergent AE (TEAE) is defined as an event that was not present prior to administration of the first dose of study treatment and present after the first administration or if it represents the exacerbation of an event that was present prior to the first administration.

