Appendix 2: Clinical Laboratory TestsI 16.2

Chemistry	Hematology
Sodium	Hematocrit
Potassium	Hemoglobin
Chloride	Red blood cells
Bicarbonate	White blood cells (WBCs)
Blood urea nitrogen (BUN)	Neutrophils
Creatinine	Lymphocytes
Glucose	Monocytes
Calcium	Eosinophils
Phosphorus	Basophils
Albumin	Platelets
Total protein	
Alkaline phosphatase (ALP)	
Aspartate aminotransferase (AST)	
Alanine aminotransferase (ALT)	
Gamma-glutamyl transferase (γGT)	
Total and direct bilirubin	
Lactic dehydrogenase (LDH)	
Creatinine clearance (eGFR by	
CKD-EPI)*	
C-reactive protein (CRP)	
Other Tests	Coagulation
Pregnancy testing	INR
	Prothrombin time

^{*} Estimated eGFR is to be calculated using the CKD-EPI Creatinine Equation 2009 calculation

ProQR Therapeutics Page 66 of 67

Investigational Product: QR-421a Protocol No. PQ-421a-004 (Version 2.0)

ProQR Therapeutics

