4.5.2. Demographic and Baseline Characteristics

Demographic and baseline characteristics, including age as collected, age category (Adult >=18 years, Children <18 years), gender, race, ethnicity, body weight (kg), height (cm), genotype (homozygous, heterozygous), randomization factor (syndromic, non-syndromic) and baseline BCVA (ETDRS letter score for both TE and CE), will be summarized for the Safety Population by treatment group using descriptive statistics.

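### One CKD-EPI 2009 eGFR equation is prescribed for all subjects although minors from 12 years are enrolled; in minors it reads higher than a height-based paediatric estimate.

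*Protocol*

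**What the plan says.** Protocol section 8.2.2 (Laboratory Evaluations) fixes the derivation: "Estimated glomerular filtration rate (eGFR) is to be calculated using the CKD-EPI Creatinine Equation 2009 calculation". Appendix 2 lists eGFR among the chemistry tests with the footnote "Estimated eGFR is to be calculated using the CKD-EPI Creatinine Equation 2009 calculation". Neither statement carries an age limit.

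Inclusion criterion 1 in section 5.3.1 admits, besides adults, "A minor (12 to < 18 years) with a parent or legal guardian willing and able to provide written permission". The SAP (section 4.5.2) expects minors in the data and tabulates "age category (Adult >=18 years, Children <18 years".

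On use, section 8.2.2 says "Eligibility of the subject to participate in the study is based in part on safety signals that may be indicated by laboratory values". It measures creatinine and BUN as well, and refers elsewhere for their interpretation: "Reference ranges for all laboratory parameters are provided in the Laboratory Manual". Height is available at baseline under section 10.6: "Subject characteristics at baseline include age, race, body weight, and height". SAP section 4.7 provides by-subject laboratory listings, and SAP section 5 says that no formal statistical analysis will be produced.

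**The concern.** The protocol prescribes a single equation for a population that includes 12 to 17 year olds. This is a stated rule, not a detail left to another document. In its standard form the equation uses creatinine, age, sex and race and has no term for body size, so a short 12-year-old and a tall adult differ only through the age and sex terms. If it reads high in minors, a derived safety value is shifted towards looking normal in the one age group for which the plan makes no provision. At stake is how an investigator or a reader of the listings interprets a minor's eGFR, at screening and afterwards.

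**Working it through.** **No figure to reproduce.** The documents state no eGFR value, cut-off or coefficient. The arithmetic below is an illustration on assumed inputs.

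**From the documents:** equation name (8.2.2, Appendix 2); age range 12 to under 18 (5.3.1); height collected at baseline (10.6).

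**Assumed:** the standard published forms, with the race factor set to 1.

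- CKD-EPI 2009 = 141 × min(Scr/κ, 1)^α × max(Scr/κ, 1)^(−1.209) × 0.993^age × 1.018 if female; κ = 0.9 (male) or 0.7 (female); α = −0.411 (male) or −0.329 (female); Scr in mg/dL.
- Height-based paediatric estimate (bedside Schwartz) = 0.413 × height in cm / Scr.

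**Worked cases (mL/min/1.73 m²)**

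- Boy, 12 years, 150 cm, Scr 1.0: 141 × (1.0/0.9)^(−1.209) × 0.993^12 = 141 × 0.880 × 0.919 = 114. Height-based: 0.413 × 150/1.0 = 62. Ratio 1.84.
- Boy, 14 years, 165 cm, Scr 1.2: 141 × 0.706 × 0.906 = 90. Height-based: 0.413 × 165/1.2 = 57. Ratio 1.59.
- Girl, 12 years, 150 cm, Scr 0.9: 141 × (0.9/0.7)^(−1.209) × 0.993^12 × 1.018 = 141 × 0.738 × 0.919 × 1.018 = 97. Height-based: 0.413 × 150/0.9 = 69. Ratio 1.41.

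**Range.** Over ages 12-17, both sexes, 140-180 cm and Scr 0.6-1.2, CKD-EPI 2009 is the higher value in every cell.

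- Largest ratio: boy, 12 years, 140 cm, Scr 0.9: 129.6 / 64.2 = 2.02.
- Smallest ratio: girl, 17 years, 180 cm, Scr 1.2: 66.4 / 61.95 = 1.07.

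**What CKD-EPI 2009 shows when the height-based estimate is 60** (set Scr = 0.413 × height/60)

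| Age, sex | Height (cm) | Scr | CKD-EPI 2009 |
|---|---|---|---|
| 12, male | 150 | 1.03 | 110 |
| 14, male | 165 | 1.14 | 96 |
| 17, male | 175 | 1.20 | 88 |
| 12, female | 150 | 1.03 | 82 |
| 14, female | 160 | 1.10 | 75 |
| 17, female | 165 | 1.14 | 71 |

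Two of these six cases, the boys of 12 and 14, read 90 or above. The count depends on the height paired with each age: a 17-year-old boy of 165 cm (Scr 1.14) would read 141 × (1.136/0.9)^(−1.209) × 0.993^17 = 94.

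**Effect of switching equation at 18.** Boy, 17 years, 175 cm, Scr 0.9: height-based 0.413 × 175/0.9 = 80; CKD-EPI 2009 = 141 × 0.993^17 = 125. A switch would raise the reported value about 1.56-fold (125.1/80.3) with creatinine unchanged.

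**The case against.** The strongest reply is that the documents supply only half of the argument. They show one equation and an enrolled paediatric age group. They do not say that the equation is unsuitable for minors, and the comparator is itself an estimate, not true filtration. That stands, so the size is given as an illustration with its range.

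A reader might go further and infer that abnormal renal function in a minor would be missed and would not reach the adverse-event tables. The documents do not support this:

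- No readable inclusion, exclusion or stopping criterion names renal function or an eGFR value. The eligibility sentence in 8.2.2 concerns laboratory values in general.
- Creatinine and BUN are reported beside eGFR. Their reference ranges are in the Laboratory Manual, which is not available here and may be age-specific.
- Section 9.4.3 makes recording of a laboratory abnormality as an adverse event depend on its clinical significance, not on a computed eGFR.
- Section 9.0 lets the investigator add tests for safety purposes.

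It can also be said that a paediatric equation brings its own artefact when a subject turns 18. The jump from about 80 to about 125 shows that this is real, and the correction has to deal with it.

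What does not fall away is the rule itself. Section 8.2.2 refers to the Laboratory Manual for reference ranges, not for the equation. A different equation for minors in that manual would contradict the protocol text.

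**Conclusion.** The point holds as a limited one. The protocol applies CKD-EPI 2009 to every subject and enrols 12 to 17 year olds without an exception. On the assumed formulas it reads about 1.1 to 2.0 times the height-based paediatric estimate, always in the direction of better renal function. Reduced function in a minor could therefore look less abnormal, and in some younger boys with a height-based estimate of 60 it could read 90 or above. That cut-off is an assumption, because the documents define no normal value.

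The consequence goes no further than that. No decision rule in the readable text depends on eGFR, other renal markers are reported with it, the number of minors is unknown, and the SAP reports laboratory data as listings without analysis. No efficacy result is affected. The correction is worth making because it is cheap and removes a known source of misreading.

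**What to change.** In section 8.2.2 and the Appendix 2 footnote:

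- Limit CKD-EPI 2009 to subjects aged 18 or over at enrolment.
- For subjects under 18 at enrolment, name a validated paediatric equation, for example the height-based bedside Schwartz equation. Another validated paediatric method would also do.
- Keep the same equation for a given subject throughout the study, so that an 18th birthday does not create an apparent change.
- Record height for minors at laboratory visits. The readable text shows height only as a baseline characteristic.

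In SAP section 4.7, add to the laboratory listing a flag for the equation used.

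Cost: a calculation setting at the central laboratory, extra height entries for minors, and two eGFR scales in one listing. No additional blood sample is needed. Since the SAP is a close-out plan, the immediate gain is correct derivation and labelling of minors' values in that listing. If no later heights exist, baseline height would have to be used and stated.
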